3.7 The effectiveness study (WP 3)

The effectiveness of the VIPP-PUF intervention is measured as a significant reduction in mental health problems (WP 3a) and a healthy weight development at age 24 months (WP 3b) among vulnerable infants, comparing infant who have received the VIPP-PUF intervention to infants, who have received care as usual.

Outcomes

The primary child outcome is child mental health at age 24 months measured by the Strengths and Difficulties Questionnaire, SDQ (178).

INFANT HEALTH

The secondary outcomes measured at child age 24 months include weight-for-length z-scores, body composition, measures of child development (Ages and Stages Questionnaire 3) and of parental well-being, parental stress, and parents' experiences of family impairment (Being a Mother- questionnaire, BaM1 (196); the Parental Stress Scale, PSS, (197, 198); and the WHO-5 well-being index, WHO-5 (199, 200)). Also, parental feeding practices, child eating behavior, parental sensitivity and parent-child interactions during mealtimes will be assessed by the Preschooler and Child Feeding Questionnaires, PFQ and CFQ (188, 189); the Child Eating Behavior Questionnaire, CEBQ (190); and by video recordings coded using the Coding Interactive Behavior, CIB (216).

Intermediate outcomes at child-age 18 months include child mental health and development measured by the Ages and Stages Questionnaire, Social-Emotional 2, ASQ-SE2 (167) and the Child Behavior Checklist, CBCL-version for children aged 1 ½ -5 years (171), which includes information on regulatory problems of eating, sleep, emotions, and behavioral and cognitive functions (42, 46-48).

The intermediate outcomes at age 18 months include measures of sensitive parenting, the Mother and Baby Interaction Scale, MABISC (at 9-10 months) (194, 195); and measures of parents' wellbeing and feeling of competence and relatedness, and parents' experiences of stress, the Parental Stress Scale, PSS, (197, 198) and the WHO-5 well-being index, WHO-5 (199, 200) as well as measures on parental feeding practices, the Preschooler and Child Feeding Questionnaires, PFQ and CFQ (188, 189).

WP 3a: The effectiveness of the intervention on the child' mental health

The effectiveness of the VIPP-PUF intervention is measured as differences scores of mental health difficulties (SDQ total score) among vulnerable infants, comparing infants receiving intervention to infants receiving care as usual. Analyses of the intermediate effect of the VIPP-PUF intervention will also be carried out by comparing scores on the CBCL and ASQ:SE2 at 18 months between the two groups.

As potential prognostic factors we include the CHNs' records of infant development and regulatory functions at age 2-4 weeks, together with their records at ages 2-3 months and 4-6 months. Parents answers to the ASQ:SE2 at child-age 9-10 months will also be included, to indicate the socio-emotional development at the baseline assessment. Other potential risk-factors will be included in

INFANT HEALTH

the analyses such as parents' socio-economic status, parental age, parental mental health problems, marital status, child gender, birth parameters. Exploratory analyses of the intervention effect on parental well-being (assessed by various repeated parental questionnaires), and to what degree that effect alternates the intervention effect on the primary outcome will be carried through.

WP 3b: Weight development

The effects of the VIPP-PUF intervention on weight development is measured as differences in weight-for-length z-scores among children with cognitive and regulatory problems at age 9-10 months who receive the VIPP-PUF intervention compared to infants who receive care as usual, CAU. Furthermore, we will investigate the effect of the VIPP-PUF intervention on body composition at age 24 months, and whether the VIPP-PUF intervention can promote decreasing levels of non-responsive parental feeding practices, higher levels of child eating self-regulation and fewer problematic child eating behaviors in the first 2 years of life.

Planned analyses include weight-for-length z-score at birth (217, 218), and the role of pre-and postnatal risk factors for childhood overweight on weight-for-length z-score at age 24 months (219, 220). Also, we plan to analyze examine weight trajectories from birth to age 9-10 months, as well as the influences of early feeding, eating, sleep and overall regulatory problems between ages 2 and 6 months as evaluated by CHN's at home visits ages 2-4 weeks, 2-3 and 4-6 months. These evaluations are based on the CHNs overall conclusion about the infants' feeding/eating/ sleep or crying and rated by the CHNs as being of concern or not (159).

The role of ethnicity, socioeconomic position of the parents and parental mental health problems will be addressed, using data from National registries or from the Child Health Database, including recorded by CHNs at home visits between ages 0 and 6 months. Specifically, we will explore whether trajectories of feeding and eating behavior and of dysregulation (eating, sleep, and emotional expression) measured between 2 and 9 months (44) and 18 and 24 months will be modified by the intervention, and to what degree eating behavior and dysregulation influences the weight-for-length-z scores at ages 24 months. Also, we will investigate the influences of parental experienced stress and parent-child relational problems at ages 9 month and 18 months on weight-for-length z scores at age 24 months.

3.8 Process evaluation- What works for the vulnerable families? (WP 4)

The aims of the overall process evaluation are 1) to document the development of the VIPP-PUF intervention, 2) to explore and analyze the implementation process of VIPP-PUF to obtain knowledge about activities and effects, and to extend the understanding of the relationship between the intervention and the outcome (221). The WP 4 of the Infant Health Study now include a specific in-depth mixed methods study, WP 4a, and an ethnographic study exploring the context of the Danish municipality child health care targeting infant families, WP 4b (See the separate WP 4 protocol description). Pursuing the second aim of the process evaluation, we will have a specific focus on vulnerable families, which include infants with major vulnerabilities regarding development and regulation, as well as vulnerable parents, i.e. parents of psycho-social adversities such as mental illness, low education, low income, and being ethnic minorities (36, 137, 138).

Data collection and analysis will run in parallel to the, the intervention planning (WP2), the pilot study (WP 2a), and the efficacy study (WP3), and includes questionnaires and interviews of the CHNs, parents and stakeholders.

Ad 1) The process of intervention development and pilot testing (WP2 and 2a) involves both CHNs and parents. We include participant observations at home visits (222), focus groups interviews (223) with participating CHNs and individual, semi-structured interviews (224) with the involved parents.

Ad) 2 Based on established process evaluation frameworks (221, 222, 225-228), we will explore recruitment to the intervention, evaluate whether the intervention is implemented as intended (fidelity), and whether and to what degree it has reached all families within the intended target group and across various risk groups (reach), as well as barriers and facilitators of implementation. Also, we will assess participant responsiveness among CHNs and parents, and their appreciation of and satisfaction with the intervention program, to get a deeper understanding of how, why and for whom the intervention was effective or not (222) (please see Table 1 for the applied process evaluation concepts).

In the in-depth mixed methods study (See separate protocol) we will thoroughly explore whether the VIPP-PUF intervention has reached all families across various risk groups and assess the particular needs and experiences among families of high vulnerability and low socio-economic position (WP4a).

INFANT HEALTH

For this part of the process evaluation, we will combine quantitative and qualitative methodologies (229, 230). Data collection and analysis run in parallel to the WP3, and will be based on questionnaires and interviews of the CHNs, parents and stakeholders in the study area concerning the implementation of the study e.g. the fidelity and reach of the intervention.

Fidelity

In order to gain a comprehensive picture of the implementation of the intervention, we will measure implementation by multiple aspects of implementation fidelity, such as structural aspects, adherence to the intervention and dosage of implementation. Also, we will explore procedural aspects, such as quality of delivery and participant responsiveness (221, 225).

Table 1. Applied process evaluation concepts

Process evaluation concept	Definition/operationalization	Data collection
Recruitment	Description of procedures used to approach and attract participants, and characteristics of participants and non-participants.	Information on child and family characteristics (see page 11-12 for elaboration) are obtained from national population registries and the Child Health Database as described in the main protocol of the Infant Health Study. Focus group interviews with CHNs will be used to nuance the understanding of the recruitment process and the nature of perceived barriers and facilitators of their recruitment of different types of families. CHN's will systematically register parents' reasons for declining the invitation. Additionally, recruitment barriers will be explored through interviews with families, who end up with non-participation either because they decline the invitation or because the CHN consider the families to be ineligible to participation.
Reach	The proportion of the target population that participates in the Infant Health Study compared to those who do not.	Data on child and family characteristics will be collected from national registries and the Child Health database. Information on the degree of participation will be

INFANT HEALTH

		collected through questionnaires among participating families.
Dose delivered	The amount of the intended units of intervention delivered by the intervention providers, e.g., number of conducted home visits.	Data will be collected through CHNs' self-monitoring checklists for each VIPP-PUF intervention session.
Fidelity	Information on the extent to which the intervention was implemented and delivered as planned (quality and integrity of the intervention delivery), including information on adaptations and reasons for adaptations.	Data will be collected through leading CHNs' recordings and through CHNs' self-monitoring checklists for each VIPP-PUF intervention session relating to all main elements of the VIPP-PUF intervention as described in the manual. Examples include the specified video recordings during daily situations at home visits; themes of the program delivered for each session and successively elaborated during the intervention period; the CHNs' use of the manualized instruction for feed-back to the parents; and the delivery of written material on sensitive parenting including sensitive responding in daily situations about e.g., eating and feeding. Also, fidelity is explored through participant observations of 10-15 home visits where the program is used and through interviews with the CHNs (see p.15-17 for elaboration of the qualitative methods).
Participant responsiveness	Information on participants' (receivers and providers) receptiveness and acceptability, how they respond to, are engaged by, and enact an intervention, their enthusiasm and interest, their judgement about the outcome, relevance, and usefulness and how far they accept the responsibility of the intervention and holds the attention.	Data will be collected through questionnaires to parents and CHNs as well as through individual interviews with parents and CHNs.

INFANT HEALTH

Barriers and facilitators of participation	Knowledge on what barriers and facilitators CHNs and parents experience when participating in VIPP-PUF.	Data on what families and CHNs experience as either facilitating or hindering their participation in the intervention will be collected through questionnaires and individual interviews with both parts.
--	---	---

Interview guides will be developed for both the focus groups and the semi-structured individual interviews. Interviews will be audio-recorded and transcribed verbatim and anonymized (231).

The separate WP 4 study (See the protocol for WP4-version January 2022) includes in-depth ethnographic explorations within the settings of municipality child health care as a context of early identification and preventive interventions, WP 4b (232-235). We will explore the current preventive practice as well as the specific implementation of the VIPP-PUF. Hereby, the study will inform a profound understanding of the complexities in the implementation process, which are needed in the interpretation of the outcomes of VIPP-PUF. The study will include the perspectives of parents, CHNs and leading CHNs regarding based on semi-structured interviews with parents, CHNs and leading CHNs, focus group interviews with CHNs and participation observations of home visits.

For further details regarding the process evaluation, please see the protocol for WP4 a and WP4 b (version January 2022).

3.9 Health economic evaluation

Health economic expertise will be consulted to plan the evaluation of the cost-effectiveness of the VIPP-PUF intervention, including data from Danish national registers and data on service use from the Child Health Database.

4 Data analysis

4.1 Analyses of qualitative data

The empirical material (i.e. transcriptions of interviews and field notes) will be analyzed following general principles for qualitative data analysis (236, 237). We will perform a systematic coding approach to identify important themes across the empirical material. We will read through and code the material in order to group the codes and categories into overall themes. Recurrent topics will be

INFANT HEALTH

identified, compared and categorized. Different forms of theory will be applied in the analyses to reach new theoretical insights e.g., on vulnerability. The analytical process will be inspired from ‘collaborative data analysis’ (238), through which different perspectives are brought to bear on the analysis and interpretation of the data. The analysis and interpretation of results will be brought into dialogue with the existing research on the research topic.

Thematic analyses of interview and focus group data will be driven by the research question and allow for more inductive analysis whereby emergent themes are also identified (236).

4.2 Statistical analyses

Statistical analyses will be carried out according to the intention to treat principle, where the participants are analyzed according to their CAU/intervention recruitment group. For continuous outcomes (including the primary outcome measured as the SDQ total difficulties score), linear mixed models will be fitted to compare the control group receiving care as usual (CAU) and the VIPP-PUF intervention group. For binary outcomes (e.g., border line/abnormal versus normal SDQ score), logistic mixed-effects regression models will be fitted to compare the control and intervention groups. All models include municipality-specific random effects, allowing for the correlation between outcomes of children from the same municipality. Likewise, cluster-specific random effects will be included.

Differences in weight-for-length between intervention and control groups will be evaluated using analysis of covariance (ANCOVA). Associations between weight-for-length z-score and selected risk factors based on their associations with infant behavior and preschool obesity in the published literature will be explored using linear regression. To assess differences in parental feeding practice and infant eating behavior between intervention and control groups, mean scores on the feeding and eating questionnaires subscales are calculated and analyzed using linear mixed models for repeated measurements, including participant-specific random effects. Further, exploratory analyses regarding feeding practices, eating behavior, and weight development will be carried out.

Other prognostic factors identified from the literature *á priori* will be included in analyses. Examples include parents’ education, employment status, household income, ethnicity, parental age, parental mental health problems and marital status (all obtained from national registers) (160); at the child level, sex, birth parameters, weight-for-length z-scores from birth to age 9 months, regulatory problems from ages 2-9 months, and ASQ:SE2 score at 9-10 months; and at the

INFANT HEALTH

municipality level, e.g., level of social disadvantage. Interaction terms will be included to explore possible differences in intervention effect (on the primary outcome SDQ score only) between gender, pre-defined subgroups based on weight-for-length z-scores 0-9 months, low versus high scores of regulatory problems 2-9 months (0-2 problems versus ≥ 3 problems of eating, sleep or emotional dysregulation); low versus high baseline ASQ:SE2 scores and parental characteristics. Also, additional analyses of effect modification will further explore the effect by different population groups (socio-economic position, family structure, and migration status).

We will use path analysis to explore whether the effect of the intervention on weight-for-length z-score at age 18 and 24 months is mediated through the above-mentioned risk factors for childhood overweight. Using path analysis, we can assess the direct effect of the intervention, corresponding to the proportion not mediated through risk factors for child overweight, and the indirect effects of the intervention, corresponding to the proportion mediated through selected risk factors for childhood overweight. The total effect is the sum of the direct and indirect effects.

(Please see the WP4 protocol, WP 4b (Version January 2022) for further details regarding the statistical analyses of the process evaluation).

Sample size re-calculation

Based on recent research (239), an updated sample size calculation has been carried out for testing the primary outcome (the SDQ total score). The mean SDQ total score at the baseline, in children with ≥ 3 problems, is expected to be 13 (182) and the intervention group is now expected to reduce the mean SDQ total score to 11 (179). Consequently, to detect a difference in the SDQ total score of 2 while assuming a standard deviation of 5.7 (239), a small cluster effect (assuming an intraclass correlation of 0.001 as there are only 3 large clusters involved), and a significance level of 0.05 and with 80% power, we need a total sample size of 306 participants (240) (21). We expect a participation rate of 85% at the baseline and a 30% dropout rate by the 24-month follow-up assessment, leaving a total of 460 children available for assessments of the primary outcomes, conditioned a recruitment of about 780 children at baseline.

5 Ethics

The study is approved by the Research Ethics Committee of the University of Southern Denmark, case nr. 20/61404; and registered and approved by the University of Southern Denmark in accordance with the Data Protection Regulation and the General Data Protection Regulation (GDPR) (EU) 2016/679; Notification number: 11.090.

The parents are informed that their participation is fully voluntary, and that families who do not wish to participate, receive care as usual. It is underscored that at any stage of the project, the parents can withdraw their participation, and then receive care as usual.

The study comprises a specified intervention as an add-on to existing services provided by CHNs in the study municipalities. Families are offered an extra home visit when the infant is 24 months of age where weight, length, and body composition are to be measured. The usual care of CHNs, which is well accepted and used by more than 90% of the population, already involves assessment, counselling and information on sensitive issues related to challenges of the health and well-being of the child e.g. mental health and overweight. In this study, the CHNs use a more standardized and specified method to address the needs of the most vulnerable infants and their families, which more than 20% of the population is offered already within the existing routines. Video-feedback which is a core ingredient of the VIPP-PUF intervention, is already frequently used among Danish CHNs as a pedagogic way of communicating infants needs to the parents (241), and experiences show that the video-feedback approach is well accepted among parents and regarded as a helpful supplement for the parents to understand the CHNs guidance (242).

Supplementary information October 2024

The project was June 2024 reviewed by the Committees on Health Research Ethics in the Capital Region of Denmark who concluded that the project should have been approved in accordance with the law of Committees and had to be paused until a formal approval from Committees on Health Research Ethics in the Capital Region of Denmark was obtained. October 2024 the project was approved and registered to be completed by 31-12-2026 with the following remarks: *“Generally, an approved project is valid throughout the accepted period, and a regular confirmation of the approval does not take place. Unless otherwise stated, the approval includes all documents listed in the approval letter. Extension of a study might be approved when applied for later. According to Danish law all health research taking place in Denmark must be approved by an Ethical Committee and must comply with Danish legislation. Please note, that "GCP" and "ICH-GCP" rules are only partially implemented in Danish law. For additional inquiries, please contact the Secretariat for*

INFANT HEALTH

the Committees on Health Research Ethics in the Capital Region at [contact] or by e-mail [contact]

6 Timeline and economy

The project was planned to be conducted from January 2020 through December 2024. Due to the COVID-19 situation and low recruitment rates, the overall study has been delayed in total 14 months and is expected to have completed the data collection by January 2025. (For a detailed and updated timeline with milestones, see Appendix 2)

The Infant Health project has received 5.8 mill DKK from the Independent Research Fund Denmark, and in total 27 mill DKK from the Novo Nordisk Foundation (Main project 20 mill.; the separate WP 4 study 7 mill.).

7 The project organization

The study is hosted at the National Institute of Public Health, NIPH, University of Southern Denmark, SDU, associated to the Center for Intervention Research and the Research group of Child and Adolescent Health (www.sdu.dk/da/sif) and led by [name] (PI) and [name] (co-PI). The PI and co-PI will take responsibility for the daily transactions of the study activities, and the NIPH will provide support for the project including the Data Manager clerical support to the trial, organizing all aspects of the postal questionnaires (mailing, tracking, and entering returned data using the study web-based data entry portal) and the web-page administrator maintaining the study webpage.

Research group

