3.2 Design

We have chosen the stepped wedge cluster randomized design (163-165) mainly for two reasons. First, it is more feasible to randomize at the municipality level as compared to the level of the individual child or CHN. An RCTs based on randomization of the individual child or nurse would be associated with more logistical demand on the individual municipality or nurse as compared to the stepped wedge design as they would be having both the intervention and the control condition running simultaneously. For practical reasons, all municipalities cannot be trained at the same time but have to be split into three groups, and with the stepped wedge design we utilize this and randomly allocate the 16 participating municipalities to the time at which their health nurses have been trained and start offering the intervention to families. Also, with the SWD spill over is reduced by the randomization of clusters as compared to individual randomization. Second, in the stepped wedge design, interventions are introduced in a stepwise manner to all participating clusters (municipalities in this case) which encourages participation for those who would otherwise have been randomized to the control condition. Initial feedback from our interactions with the municipalities reveals that their motivation is strongly associated with being able to offer the intervention, as many municipalities prioritize early intervention highly. Also, with the stepped wedge design control families are recruited in the early phases of the trial, which enhances the recruiting of a control group with the level of usual care offered at the beginning of the trial. In the control period no participants receive intervention and sequential random crossover to the intervention cannot be reversed (166).

An important advantage of the stepped wedge design is that families only need to consent to participate in a research study and not to be randomized. In our experience this makes a big difference not only to the families, but also the front personnel who are recruiting the families. With a longer recruitment period and higher expected acceptance rates, the stepped wedge design will

INFANT HEALTH

[figure not shown]

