result in a larger sample size and less frustration about recruitment among the CHNs who find it very hard to deliver standard care to families, when they have introduced an intervention, they believe is superior. Thus, we believe that the stepped wedge design is associated with the least dropout.

On a practical level, the 16 participating municipalities will be randomly distributed into three clusters (6+5+5), and clusters will be randomized to initiate intervention at three different time points, according to the stepped-wedge design (see Figure 1, flow diagram revised October 2022) (Detailed overview of the design, see Appendix 1).

Figure 1. CONSORT diagram

INFANT HEALTH

Randomization and screening (PUF) at child-age 9-10 months

According to the randomization of municipalities, all children assessed to have ≥ 3 problems will function as controls and receive care as usual from Step 0 until the municipalities initiate the intervention in Step 1- 3, respectively.

Recruitment of municipalities, children, and parents

INFANT HEALTH

[figure not shown]
All municipalities that have implemented the basic PUF-program are invited, and the leading CHNs from the becoming study municipalities are invited to join the study planning group as key stakeholders.

In the participating municipalities, the parents of children becoming 9-10 months in the study period are informed about the project by the CHNs, and via written folders and information on the study home page (<https://www.sdu.dk/da/sif>). At the scheduled home visit at child ages 9-10 months, the CHNs complete PUF-assessment and offer the parents feedback in accordance with the basic PUF-program and the existing routines. All parents of children who have been assessed to have three or more problems are offered extended service, in the control phase of the study this is delivered in accordance with the existing routines of the CHNs in the particular municipalities (care as usual), whereas the CHNs offer the VIPP-PUF intervention to parents in the intervention phase. The CHN informs all parents of infants full-filling the study criteria of inclusion about the details in the Infant Health project, and if parents are interested, they are invited for participation by e-post. Parents make their final agreement for participation by answering the web-based questionnaires at the study website.

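### No effectiveness model in Section 4.2 adjusts for step, period or calendar time, so in this one-way stepped wedge the VIPP-PUF estimate is partly confounded with any secular trend

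*Protocol*

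**What the plan says.** The Protocol and the combined protocol and SAP carry the same Section 4.2. For continuous outcomes, including the primary SDQ total score, "linear mixed models will be fitted to compare the control group receiving care as usual (CAU) and the VIPP-PUF intervention group". Binary outcomes get a logistic mixed model with the same contrast. On random effects: "All models include municipality-specific random effects, allowing for the correlation between outcomes of children from the same municipality". And: "Likewise, cluster-specific random effects will be included". Weight-for-length is compared by ANCOVA. Feeding and eating scores use a repeated-measures mixed model, in which the repeats are over child age, not calendar period. Covariates are introduced as "Other prognostic factors identified from the literature", followed by examples at family, child and municipality level. None of these is step, period, recruitment date or calendar time.

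Section 3.2 describes the design. The 16 municipalities are split 6+5+5 and start the intervention at three time points. Eligible children "function as controls and receive care as usual from Step 0 until the municipalities initiate the intervention" in Steps 1 to 3. The "sequential random crossover to the intervention cannot be reversed", and "with the stepped wedge design control families are recruited in the early phases of the trial".

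**The concern.** In a one-way wedge, being an intervention child goes with being recruited late. The randomised order of crossover protects the comparison only when intervention and control children are compared within the same period. A model without a period term also uses the early-versus-late contrast. Municipality and cluster effects do not help: they are constant over time, so they describe differences between places and not changes across them.

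The protocol reports events that could produce a trend (Section 3.1):

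- pandemic disruption;
- brush-up PUF courses;
- seven project nurses added to support identification;
- a pause in data collection from June to October 2024.

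A child turns 24 months about 14 to 15 months after the 9-10 month visit, so the pause falls on children first seen in about March to August 2023. If the recruitment window (16 August 2021 to 31 October 2023, 806 days) is cut into four equal periods, the last starts on 12 April 2023. Most or all municipalities would then be in the intervention phase. The step dates are an assumption, because the content of Appendix 1 is not in the text available to this review. The documents give neither a direction nor a size for any effect of these events on SDQ.

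At stake is whether the primary result can be read as an effect of VIPP-PUF or partly as a change over time.

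**Working it through.** **The plan's own figure.** Section 4.2 uses a difference of 2, SD 5.7, alpha 0.05, 80% power and ICC 0.001, and arrives at 306 children. Taking a two-sided test and 1:1 allocation (neither is stated):

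n per arm = 2 × (1.960 + 0.842)² × 5.7² / 2² = 127.5, so 128 per arm and 256 in total.

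The design effect is 1 + (m − 1) × 0.001, but the cluster size m is not given. Reaching 306 needs m of about 201, or rounding up to three whole clusters of 102. The figure therefore cannot be fixed from the text, which does not show that it is wrong. What matters here is that the calculation mentions no allowance for period effects. The flow agrees: 780 × 0.85 × 0.70 = 464, against the stated 460.

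**Layout.** Municipalities in each condition, assuming that the group of six starts first:

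| Step | VIPP-PUF | CAU | Share on VIPP-PUF |
|---|---|---|---|
| 0 | 0 | 16 | 0 |
| 1 | 6 | 10 | 0.375 |
| 2 | 11 | 5 | 0.69 |
| 3 | 16 | 0 | 1.00 |

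Both conditions are present in Steps 1 and 2, so confounding is partial. The correlation of exposure with period is 0.74.

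**Share of a linear drift that enters.** With equal period and municipality sizes:

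- mean step of intervention children: (6×1 + 11×2 + 16×3)/33 = 2.30
- mean step of control children: (10×1 + 5×2)/31 = 0.65
- difference: 1.66 of the 3 steps, or 55% of the total drift.

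Generalised least squares with a municipality random intercept gives 56%, 59% and 62% at ICC 0.001, 0.02 and 0.05. The share rises with the ICC because more weight moves to before-after comparisons within municipalities.

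**Bias and type I error with no period term.** N = 460, SD 5.7, no true effect, no covariates. Standard errors are 0.533, 0.544 and 0.547 at the three ICCs. Type I error = Φ(−1.96 + b/SE) + Φ(−1.96 − b/SE), where b is the bias.

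| Hypothetical drift | Bias (ICC 0.001 / 0.02 / 0.05) | Type I error |
|---|---|---|
| 0.5 points in total, linear | 0.28 / 0.29 / 0.31 | 8.2 / 8.4 / 8.7% |
| 1 point in total, linear | 0.56 / 0.59 / 0.62 | 18.1 / 19.2 / 20.3% |
| 2 points in total, linear | 1.11 / 1.18 / 1.23 | 55.0 / 58.3 / 61.5% |
| 1 point, last period only | 0.49 / 0.52 / 0.54 | 15.0 / 15.8 / 16.7% |

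The 2-point row equals the whole target effect and is an upper case. If baseline covariates absorbed half of a 1-point drift, the 0.5-point row would apply. With fixed period effects the bias is zero in every row, because each row gives all municipalities the same drift.

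**Unequal recruitment.** Four other splits over the periods (40/20/20/20, 20/20/20/40, 15/35/35/15 and 35/15/15/35) let 38 to 76% of a linear drift in. Type I error for a 1-point drift is then 11 to 30%.

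**Precision with period effects.** Period explains 55% of the variance in exposure, so the variance of the estimate rises by about 1/(1 − 0.55) = 2.2. The least-squares value at ICC 0.001 is 2.24, so SE = 0.533 × √2.24 = 0.797. Power for 2 points = Φ(2/0.797 − 1.96) = Φ(0.55) = 71%, against 96% without period effects.

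**The case against.** Section 4.2 is a summary and not a model equation. Its covariate list is open, the design section cites stepped-wedge literature, and detail is deferred to Appendix 1 and a published protocol. On this view, time adjustment is unstated rather than excluded. It is true that nothing forbids a time term. But period is a design term, not a prognostic factor drawn from the literature, and the citations support the choice of design. If the point stays open, two materially different primary analyses remain available after the data are seen.

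A second objection is that no SDQ trend is documented. The courses and added nurses bear mainly on identification, the pandemic is tied to recruitment, and the pause is first a missing-data or late-assessment problem. Baseline covariates such as ASQ:SE2 at 9-10 months may absorb part of a case-mix drift. This stands as a limit on the size of the problem. It does not cover a trend in usual care, pandemic conditions or outcome collection.

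Third, zero bias with period effects holds only for a trend shared by all municipalities, and Section 3.1 describes uneven change. This is correct. If half the municipalities had a 1-point drift, the period-adjusted bias would average zero over which half it was, but could reach about a third of a point either way for one particular half. That supports a sensitivity analysis. It is no argument for leaving period out.

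**Conclusion.** The concern holds and should be settled before the primary analysis. The omission is plain in the text and applies to every effectiveness model in Section 4.2. Under the models as written, part of any secular trend is counted as intervention effect.

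The direction and size of any actual bias are unknown. The figures show the mechanism under assumed drifts, four periods, equal municipality sizes and no covariates; they do not measure this trial's bias. In the central illustration, a drift of 1 point over the whole trial moves the estimate by more than a quarter of the 2-point target and raises the type I error to between three and four times its nominal level.

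**What to change.** Pre-specify fixed effects for recruitment step or period (Steps 0 to 3 of Appendix 1) in the primary SDQ model and in every other effectiveness model: logistic, ANCOVA and repeated-measures. Keep the municipality random intercept. State that the period-adjusted estimate is the primary result. A municipality-by-period random effect can be added as a sensitivity analysis for uneven trends; with 460/(16 × 4), or about 7, children per municipality-period, it is too thinly supported to be the main model. Restate power with a stepped-wedge formula that includes period effects.

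The change needs SAP wording and a new power calculation. It needs no new data, since recruitment dates are already held. The real cost is precision. With equal periods and no covariates, power for 2 points with period effects is:

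| Children assessed | ICC 0.001 | ICC 0.02 | ICC 0.05 |
|---|---|---|---|
| 460 (planned) | 71% | 66% | 62% |
| 471 (available, October 2024) | 72% | 67% | 63% |

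Across the unequal splits at 460 children the range is 46 to 84%. Reaching 80% with equal periods would need about 575 to 740 assessed children, and recruitment was due to end on 31 October 2023. Covariates could recover some of the loss: if they explained 10% or 20% of SDQ variance (an assumption), power at 460 children and ICC 0.001 would be about 75% or 80%. The higher power without period effects is valid only if there is no secular trend, so the restated figure is the one to use when interpreting a null result.
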